10.1. Statistical Hypotheses

Primary endpoint 1.1 is to assess the diagnostic accuracy of the Truenat MTB assays for MTB detection among individuals undergoing evaluation for pulmonary TB, overall and per sample, separately for smear-positive and smear-negative TB samples using a culture reference standard.

Primary endpoint 1.2 will estimate diagnostic accuracy of the Truenat RIF assay for RIF resistance detection among individuals undergoing evaluation for pulmonary TB and DR TB, using a reference standard of phenotypic/genotypic DST i.e. MGIT SIRE and sequencing for RIF resistance.

Secondary endpoints will compare the diagnostic accuracy of the Truenat MTB assays and RIF assay to that of Xpert MTB/RIF, using a reference standard of culture for TB diagnosis and MGIT SIRE and sequencing for detection of RIF

resistance. Additionally, the trial will assess patient important outcomes, including: i) time to detection of TB and RIF resistance, ii) yield over smear microscopy and Xpert MTB/RIF and iii) upfront diagnosis of RIF (reflex testing on all Truenat MTB or MTB Plus positive versus current standard of smear-positive reflexed to Xpert MTB/RIF based on risk factors).

10.2. Sample Size Determination

The sample size was chosen to achieve high confidence in the accuracy estimates for MTB-detection and RIF resistance detection for the overall multi-country trial for which the Indian trial is one of the countries.

Based on an expected sensitivity of Truenat MTB plus for detection of TB among smear-negative/culture-positive cases of 67% (based on preliminary data), 80 smear-negative/culture-positive cases would be required to achieve a total width of the 95% confidence interval of 20% (95%CI: 57 to 77). Assuming a TB prevalence of 20% and a prevalence of smear-negative/culture-positive cases among TB cases of 30%, the total number of subjects to be enrolled would be 1,333. To account for losses, this is inflated by 20%, yielding a final sample size of 1,666 participants under investigation for TB overall.

In India, two thirds of these trial participants will be recruited i.e. $n = 1,110$ thus 67 smear-negative/culture-positive cases and a 95% confidence interval of 21% could be achieved (95%CI 55 to 79).

The other one-third of enrolled participants ($n = 556$) will be recruited in three other countries in order to provide geographic variation.

The secondary objective of determining diagnostic accuracy of RIF resistance by Truenat MTB is based upon an expected Truenat RIF sensitivity of 95% with a confidence interval of 10% (90-100%), requiring $n=37$ RIF-resistant participants detected. Assuming a prevalence of 20% culture-positive TB cases detected across all presumed TB cases, and 2.8% RIF resistance amongst all culture-positive TB cases and 12% prevalence of RIF resistance amongst TB retreatment cases, we predict 1,542 re-treatment patients would thus need to be enrolled. While the prevalence of culture-positive TB cases may be higher if enrolment is conducted at a drug-resistance TB referral clinic, we conservatively accept that this may not be the case. As such, we may not reach sufficient sample size to allow analysis of secondary objectives in this trial. Detection of RIF resistance will be continually monitored throughout the trial, and any possible shortfall will be supplemented with a future sub-study, if needed, using confirmed RIF-resistant sputum samples from the FIND specimen bank of cryopreserved samples. We will place an enrolment cap of 200 enrolled participants in the drug resistance group for the entire trial, in order to not undermine the primary objective of enrolment of smear-negative culture

positive TB cases through inadvertent over-enrolment of DR cases who are more likely to be smear-positive culture-positive.

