3.3. End of Trial Definition

A participant is considered to have completed the trial if he/she has completed the last visit. The end of the trial is defined as the date of the last visit of the last participant in the trial globally.

4. Trial Population and Eligibility

Trial population: Adults with presumptive tuberculosis disease.

Trial/sample size: Target enrolment for the multicentre trial is 1,666 participants enrolled.

Setting: In India, a total of 9 DMC will represent the intended settings of use including urban, peri-urban/hilly, tribal and rural sites with low and high throughput laboratories in India. Based on these characteristics the following numbers of presumptive TB cases, including smear-positive cases, are anticipated per DMC type (Table 2).

Table 2. Types of designated microscopy centres in India

S.No	DMC type	Nr. subjects with TB symptoms with sputum examination/month*	% Smear-positive among subjects with TB symptoms/month*
1	Low volume DMC (in health posts/UPHC)	40 (30 - 50)	2% - 3%
2	High volume DMC (in UPHC)	120 (100 - 150)	6% - 9%
3	High volume DMC (in Tertiary care/hospitals for chest diseases or TB)	300 (200 - 500)	10% - 12%

*Under routine conditions.

Participating DMC have been selected based on the following requirements:

- Smear microscopy must be available
- Xpert MTB/RIF must not be available
- At least 10 hours of electricity available (Trueprep Auto 10h per charge for 16 runs; Truelab UnoDx 4h per charge for 8-10 runs)
- At least 10 sputum samples collected per week, i.e. ~2 samples per day
- Have easy access to a reference laboratory with capacity to perform reference standard tests to ensure timely and high quality results

Given the important role of the private sector in India, 1 private laboratory will be included in the trial which is an MDR reference hospital.

Additionally, 3 other global sites will be setup in South America, Eastern Europe and Asia/Africa to achieve a wider geographic variation. These sites will be outpatient TB clinics at district or regional health facilities.

In order to meet enrolment targets (n= 1,666 total enrolled participants: India will enrol n = 1,110; other global sites will enrol n = 556).

All sites will need to be able to attain informed consent and obtain four sputum samples per patient for index and reference tests (as per sample flow in Figure 2). Participating centres must also have sufficient space to accommodate the Truenat instruments.

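### Section 10.2 misstates the India precision: the printed width and limits disagree, and the 67 cases leave out the 20% loss, which would make them about 53 with an interval about 25 points wide

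*Protocol*

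**What the plan says.** Section 10.2 sizes the trial on the precision of sensitivity in smear-negative/culture-positive TB. Expected sensitivity is set for "smear-negative/culture-positive cases of 67% (based on preliminary data"), and 80 such cases are said to be "required to achieve a total width of the 95% confidence interval of 20% (95%CI: 57 to 77"). The yield comes from this: "Assuming a TB prevalence of 20% and a prevalence of smear-negative/culture-positive cases among TB cases of 30"%. That leads to 1,333 participants, and then: "To account for losses, this is inflated by 20%, yielding a final sample size of 1,666 participants under investigation for TB overall".

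Two thirds of that total are assigned to India, with this expected result: "thus 67 smear-negative/culture-positive cases and a 95% confidence interval of 21% could be achieved (95%CI 55 to 79").

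Section 4 repeats the split: "In order to meet enrolment targets (n= 1,666 total enrolled participants: India will enrol n = 1,110; other global sites will enrol n = 556").

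Section 10.2 also limits the second enrolment group: "We will place an enrolment cap of 200 enrolled participants in the drug resistance group for the entire trial". The reason given is to protect enrolment of smear-negative cases, because drug-resistant cases are more often smear-positive and culture-positive. No sentence says whether this group sits inside the 1,666 or is additional to it. Section 10.5.2 fixes the Wilson score as the interval method.

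**The concern.** Three features of the India sentence do not fit together. The stated width and the stated limits differ by 3 points. The stated width looks too small for 67 cases, since 80 cases are said to give 20 points. And India would yield 67 cases from two thirds of the participants, when two thirds of 80 is about 53.

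What is at stake is the country-level precision claim. A reader would expect a larger India case count and a tighter interval than the plan's own inputs support. A related question is whether Drug Resistant group participants, if counted within the 1,666, have the same 6% yield that the calculation applies to everyone.

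**Working it through.** **Inputs.** Sensitivity p = 0.67, TB prevalence 0.20, smear-negative share 0.30, loss 20%, total 1,666 and India 1,110 (all Section 10.2). Interval method: Wilson (Section 10.5.2). Wald is shown beside it. z = 1.96.

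**Formulas.**
- Yield per participant: 0.20 x 0.30 = 0.06.
- Wald width: 2z√[p(1−p)/n].
- Wilson width: 2z√[p(1−p)/n + z²/(4n²)] / (1 + z²/n).

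**Step 1: the overall figures reproduce.**
- 80 / 0.06 = 1,333, and 1,333 / 0.8 = 1,666.
- The 80 is therefore the count after loss: 1,666 x 0.8 x 0.06 = 80.
- At n = 80: Wald 56.7 to 77.3 (width 20.6); Wilson 56.1 to 76.3 (width 20.2). This agrees with the stated 57 to 77 and about 20 points.

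**Step 2: the India figures do not.**
- Printed limits: 79 − 55 = 24 points, against a printed width of 21.
- 1,110 x 0.06 = 66.6, so 67 arises only with no loss. On that basis the whole trial would yield 1,666 x 0.06 = 100 cases, not 80.
- At n = 67: Wald 55.7 to 78.3 (width 22.5); Wilson 55.1 to 77.1 (22.0); Clopper-Pearson width 23.5. None gives 21 or 24.
- A width of 21 needs about 77 cases (Wald) or 74 (Wilson). A width of 24 corresponds to about 59 (Wald) or 56 (Wilson).

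**Step 3: India on the basis used for the 80.**
- 1,110 x 0.8 x 0.06 = 53.3 cases, which is two thirds of 80.

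| India cases | Basis | Wald 95% CI (width) | Wilson 95% CI (width) |
|---|---|---|---|
| 67 | no loss | 55.7 to 78.3 (22.5) | 55.1 to 77.1 (22.0) |
| 53 | 20% loss | 54.3 to 79.7 (25.3) | 53.6 to 78.1 (24.6) |

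- Cross-check: the other sites give 556 x 0.8 x 0.06 = 26.7, and 53.3 + 26.7 = 80.

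**Step 4: the Drug Resistant group, conditionally.** Suppose its participants count within the 1,666 and the cap of 200 is filled. The protocol gives no smear-negative/culture-positive yield for them, so the yield y is an assumption. Overall cases = 1,466 x 0.8 x 0.06 + 200 x 0.8 x y = 70.4 + 160y.

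| Assumed y | Overall cases | Wilson width |
|---|---|---|
| 0% | 70.4 | 21.5 |
| 3% | 75.2 | 20.8 |
| 6% | 80.0 | 20.2 |
| 10% | 86.4 | below 20.2 |

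Break-even is y = 6%.

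**The case against.** The sentence says only what could be achieved, so 67 might be meant as a ceiling with no losses. That reading would excuse the count but not the width: 67 cases still give 22.0 to 22.5 points, and the limits still contradict the 21. The ceiling would also stand unmarked beside an overall figure that is net of loss. Losses are expected in this design, since Sections 5.3.5 and 10.5.2 exclude contaminated cultures and indeterminate index results from the accuracy analyses.

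The printed limits of 55 to 79 also lie within about a point of the loss-adjusted ones, so the main errors are the 21 and the 67. That is fair. So is the point that the India sentence does not drive the sample size: Section 10.2 says the size was chosen for the overall multi-country trial, and Section 10 sets no India precision target.

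Two stronger readings are tempting, and the documents support neither.

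- **The overall target of 80 is missed because of the Drug Resistant group.** Counting within the 1,666 is not enough. The 200 is a cap and not a target, and a shortfall also needs a yield below 6%, for which no figure is given. The protocol describes these cases as more often both smear-positive and culture-positive, and higher culture positivity can offset a lower smear-negative share. As an assumed illustration, 60% culture-positive x 10% smear-negative = 6%. Even at zero yield with a full cap, the Wilson width goes from 20.2 to 21.5, against a goal that Section 10 describes as approximately 20%.
- **India would supply 67 of 80 cases, or 84%.** That ratio mixes a count without loss and a count with loss. The like-for-like pairs are 67 of 100 and 53 of 80.

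**Conclusion.** The India precision statement is wrong as printed. Its width contradicts its limits, neither fits 67 cases, and the 67 omits the loss allowance built into the 1,110. With the plan's own inputs (67% sensitivity, 6% yield, 20% loss), India expects about 53 cases. The 95% interval is about 54 to 78 by Wilson (24.6 points) or 54 to 80 by Wald (25.3 points). The stated width is therefore about 4 points too small and the count about a quarter too high (67/53 = 1.26). If losses fall below 20%, the Wilson width lies between 24.6 and 22.0 points and still does not reach 21.

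The error is confined to the country-level statement. The total of 1,666 is correctly derived from its inputs.

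The Drug Resistant group question is secondary and conditional. If the group counts within the 1,666 and the cap fills, the overall count is about 70, 75 or 80 for an assumed yield of 0%, 3% or 6%, and above 6% there is no shortfall. What the protocol lacks is a statement of where this group is counted.

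**What to change.** In Section 10.2, replace the India figures with about 53 evaluable smear-negative/culture-positive cases after the 20% loss, and a 95% CI of about 54 to 78 (Wilson, width about 25 points). If the figure without loss is kept as a best case, label it as such and print its own interval: 67 cases, about 55 to 77, width 22 points.

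Add one sentence saying whether Drug Resistant group participants count within the 1,666. If they do, give the assumed smear-negative/culture-positive yield for that group and a range for the overall count. Do not print 70 as the expected figure, since it rests on an unsupported zero yield. Adjust the India figure for any of these participants enrolled there: 53 for India beside 70 overall would be consistent only if all 200 were enrolled elsewhere.

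The cost is a text change. Enrolment and analysis stay as they are, and the stated India precision becomes somewhat less favourable.

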Eligibility criteria	
Individuals who have symptoms consistent with pulmonary TB presenting to participating centres will be assessed and asked to participate. Participants will be categorised into 2 groups:
 
Case Detection group - Only participants who have not received any form of TB treatment within the prior 60 days will be enrolled.
 
Drug Resistant group – Non-converting TB cases presumed to be at risk of drug-resistance.

Primary outcomes	
1. Primary outcomes
 
1.1. Sensitivity of the Truenat MTB assays (including analysis by smear-status and by sample).
 
1.2. Specificity of the Truenat MTB assays (including analysis by sample).
 
1.3. Sensitivity of the Truenat MTB-RIF Dx assay.
 
1.4. Specificity of the Truenat MTB-RIF Dx assay.

Secondary outcomes	
2. Secondary outcomes
 
2.1. Sensitivity of the Truenat MTB assays and MTB-RIF Dx assay compared to Xpert MTB/RIF.
 
2.2. Specificity of the Truenat MTB assays and MTB-RIF Dx assay compared to Xpert MTB/RIF.
 
2.3. Patient important outcomes (see details in section Patient important outcomes under Statistical analysis plan).

Trial duration	Approximately 12 months
Time schedule	Trial start expected Q4-2018 with enrolment completion by Q2-2019. Follow-up after 2 months and testing of discordant cases completed Q4-2019.
GCP statement	All studies sponsored by FIND will be conducted in accordance with ICH-GCP Guidelines (ICH-GCP E6 R2), to the extent possible in the research setting as well as all national legal and regulatory requirements (as apply).

Schedule of Activities

Procedure	Enrolment		Follow-up visit 1	Notes
	Day 1	Day 2	Day 56 (±14)	
Informed consent	X			
Inclusion and exclusion criteria	X			
Demography	X			
Medical history (includes prior history of TB)	X			
Sputum sample collection	X	X*		
Blood sample collection (optional)	X			HIV testing will be offered to all participants as part of the trial procedures, unless a prior result is available (see Section 8)
AE/SAE review	←=====→			
Assess interval medication history			X	
 • Culture-negative, Truenat MTB (and/or MTB plus) and Xpert discordant cases. • 20% of Case Detection Group participants with negative results for all test, including culture

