1.3 Benefit/Risk Assessment

Knowledge gained from this trial may benefit society by improving TB diagnosis. Trial participants may directly benefit from the trial because they will be provided with a higher standard of TB diagnostic care than may be routinely available to them.

Given the minimal risks associated with this trial and the potential benefits to society and individuals, the benefits outweigh the aggregated risks. As for any clinical trial, there is a possibility of unknown and unforeseen risk; that possibility is small for this trial. If unforeseen risks are recognized during the trial, then FIND, trial partners, IRBs/ethics committees, and participants must be provided with relevant information.

2 Trial Objectives and Endpoints

Table 1. Trial objectives and endpoints

Objectives	Endpoints
1. Primary	
1.1. Estimate diagnostic accuracy of the Truenat assays (MTB and MTB Plus) for Mycobacterium tuberculosis (MTB) detection among individuals undergoing evaluation for pulmonary TB, overall and per sample, separately for smear-positive and smear-negative TB samples using a culture reference standard.	1.1.1. Sensitivity of the Truenat MTB and MTB Plus assays (including analysis by smear-status and by sample). 1.1.2. Specificity of the Truenat MTB and MTB Plus assays (including analysis by sample).
1.2. Estimate diagnostic accuracy of the Truenat MTB-RIF Dx assay for RIF resistance detection among individuals undergoing evaluation for pulmonary TB and DR TB, using phenotypic/genotypic drug susceptibility testing (DST) ¹ .	1.2.1 Sensitivity of the Truenat MTB-RIF Dx assay 1.2.2 Specificity of the Truenat MTB-RIF Dx assay
2. Secondary	
2.1. Compare the diagnostic accuracy of the Truenat assays (MTB and MTB Plus) and MTB-RIF Dx assay to that of Xpert MTB/RIF, using a reference standard of culture for TB diagnosis	2.1.1. Sensitivity of the Truenat MTB and MTB Plus assays and MTB-RIF Dx assay compared to Xpert MTB/RIF

¹ All samples that exhibit RIF resistance, as determined by either phenotypic DST or Truenat RIF, will be sent for DNA sequencing to determine the mutations responsible for drug resistance. A subset of drug sensitive samples, of approximately matching sample size, will be randomly selected for sequencing, to act as a comparator sequence

and phenotypic/genotypic DST for detection of RIF resistance.	2.1.2. Specificity of the Truenat MTB and MTB Plus assays and MTB-RIF Dx assay compared to Xpert MTB/RIF

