10.5.2. Analysis of Primary Outcomes

Analyses of the diagnostic accuracy of the index test will be done according to the case definitions. Table 6 summarizes the way diagnostic tests results are usually reported when comparing the index test results to a reference standard. Based on the definitions in the table, the following values are defined:

Sensitivity = $TP / (TP + FN)$

Specificity = $TN / (FP + TN)$

Table 6. Definition of classification metrics

Test result	Case definition			
		TB	Non-TB	Total
	Detected	TP	FP	TP + FP
	Not detected	FN	TN	FN + TN
	Total	TP + FP	FP + TN	All

Abbreviations: TB=true positive, FP=false positive, FN=false negative, TN=true negative

Only patients with uncontaminated culture results and without indeterminate test results will be included in the analysis of performance characteristics for MTB detection. Similarly, such patients will contribute to the analysis of the performance characteristics for RIF detection. For each point estimate, a 95% confidence interval will be derived based on Wilson score. Missing data and invalid results will be reported in the descriptive tables, and will not be imputed.

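### Section 10.2's 37 RIF-resistant cases give a 95% interval about 14 to 16 points wide, not the stated 10, and the section calls RIF accuracy secondary where the rest of the protocol lists it as primary

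*Protocol*

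**What the plan says.** Section 10.2 sets the RIF target with an "expected Truenat RIF sensitivity of 95% with a confidence interval of 10% (90-100%), requiring $n=37$ RIF-resistant participants detected". From this, using 20% culture positivity and 12% RIF resistance among retreatment cases, it derives 1,542 retreatment patients. It then limits the relevant group: "We will place an enrolment cap of 200 enrolled participants in the drug resistance group for the entire trial". It admits the likely consequence: "As such, we may not reach sufficient sample size to allow analysis of secondary objectives in this trial". Detection of resistance is to be monitored, and a shortfall may be made up in a later sub-study on banked specimens.

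The interval method is fixed in section 10.5.2: "For each point estimate, a 95% confidence interval will be derived based on Wilson score".

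On status, section 10.2 treats RIF accuracy as a secondary objective. The synopsis lists it among the primary outcomes ("1.3. Sensitivity of the Truenat MTB-RIF Dx assay", with specificity as 1.4). Table 1 in section 2 gives it as primary objective 1.2: "Estimate diagnostic accuracy of the Truenat MTB-RIF Dx assay for RIF resistance detection among individuals undergoing evaluation for pulmonary TB and DR TB". Section 10.1 likewise calls it primary endpoint 1.2.

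**The concern.** A precision target consists of an expected value, an interval width, a confidence level and a number of cases. Any three determine the fourth, and here the four do not agree: the number of cases is about half of what the other three require. Someone reading section 10.2 would conclude that 37 resistant cases are enough to report sensitivity to within 5 points either way.

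The error carries into the 1,542. It also affects the benchmark for a shortfall, because 37 is the only number of resistant cases that the section gives. The conflicting label adds to this. The admission that the sample may be too small is worded for secondary objectives, so a reader who takes RIF accuracy as primary, as three other places say, cannot tell whether it applies.

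**Working it through.** **Inputs.** From section 10.2: expected sensitivity p = 0.95; total width 10 points (half-width h = 0.05); 37 cases; culture positivity 20%; RIF resistance 2.8% among all culture-positive cases and 12% among retreatment cases; 1,666 enrolled with 20% losses; cap of 200. From section 10.5.2: 95% Wilson interval. The RIF sentence does not repeat the confidence level. 95% is the level used elsewhere in section 10 and is assumed here.

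**1. Trying to reproduce 37.** Wald formula, n = z²p(1−p)/h²:
- two-sided 95%: 1.96² × 0.95 × 0.05 / 0.05² = 73.0, so 73
- two-sided 90% (the same as one-sided 95%): 51.4, so 52
- one-sided 90%: 31.2, so 32
- half-width of 10 points instead of 5: 18.2, so 19

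The smallest n with a total width of 10 points at p = 0.95 is 83 by Wilson and 94 by Clopper-Pearson. None of these is 37. That number appears only if an input is changed: h = 0.07 gives 37.2; p = 0.975 gives 37.5; and 37 positives out of 37 give about 91 to 100%, which is an observed sensitivity of 100%, not 95%.

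**2. What 37 cases give at p = 0.95.**

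| Method | 95% interval | Width (points) |
|---|---|---|
| Wald | 88.0 to 102.0 | 14.0 |
| Wilson | 82.9 to 98.7 | 15.8 |
| Clopper-Pearson | 82.4 to 99.5 | 17.1 |

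**3. What a 10-point width needs.** 73 by Wald, but 73 cases have a Wilson width of 10.7 points. By Wilson, 83 cases give 88.0 to 98.0.

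**4. Comparison with the MTB calculation in the same section.** 80 cases at 67% have a Wilson width of 20.2 points, which agrees with the 20% stated there. By the same standard the RIF figure would be 83.

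**5. Retreatment patients.** The yield is 0.20 × 0.12 = 0.024.
- 37 / 0.024 = 1,541.7, the plan's 1,542
- 73 / 0.024 = 3,041.7
- 83 / 0.024 = 3,458.3

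**6. Resistant cases the design can expect.** Take the 200 as part of the 1,666 (an assumption). The other 1,466 contribute 1,466 × 0.20 × 0.028 = 8.2.

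| Capped group of 200 | Its cases | Total before losses | After 20% losses | Wilson width at 95% (points) |
|---|---|---|---|---|
| 20% culture-positive, 12% resistant | 4.8 | 13.0 | 10.4 | about 29 to 33 |
| 100% culture-positive, 12% resistant | 24.0 | 32.2 | 25.8 | about 17 to 20 |

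If the 200 came on top of the 1,666, the first row would be 14.1 before losses and 11.3 after. To reach 37, the product of culture positivity and resistance in the 200 would have to be (37 − 8.2)/200 = 14.4% before losses, or (46.25 − 8.2)/200 = 19.0% after 20% losses (37/0.8 = 46.25). The section's assumption is 2.4%.

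**The case against.** The protocol does not conceal the problem. Section 10.2 says the number may not be reached, explains the cap, promises monitoring and names a possible sub-study. Total enrolment is set by smear-negative, culture-positive cases; 37 and 1,542 set neither the enrolment nor any decision rule. All of that stands, and it confines the point to a wrong precision statement and a conflicting label. It does not make the statement right: the admission of a shortfall gives no expected count or width and is measured against a target that is itself too low.

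A reader might infer that the trial will produce only 10 to 13 resistant cases. The documents do not support that as a forecast. It applies the section's admittedly conservative 20% culture positivity, and 12% resistance from retreatment cases in general, to a group that section 4.1 defines as treatment failures. Section 10.2 itself says such cases are more likely to be smear- and culture-positive, and one site is an MDR reference hospital. Nor is 26 to 32 a ceiling, since it still holds resistance at 12% and the protocol gives no figure for failures.

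A reader might also take 37 as a formal trigger for the sub-study. No numerical trigger is stated; 37 is only the one number against which a shortfall could be judged.

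**Conclusion.** The statement in section 10.2 is wrong as written. At 95% sensitivity and 95% confidence, 37 cases give a width of 14 points (Wald) or 16 points (Wilson), against the stated 10. The required number is 73 or 83, and 83 is the one that matches the planned analysis. This rests only on the section's own expected value and width and on the 95% level used elsewhere in section 10.

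The contradiction over primary or secondary status is also established, with section 10.2 the outlier against the synopsis, Table 1 and section 10.1.

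The number of resistant cases the trial will yield is not established. It can only be shown as a range that depends on culture positivity and resistance in the capped group. The finding does not show that the enrolment of 1,666 or the cap is wrong.

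**What to change.** In section 10.2, do one of two things:
- keep 37 and 1,542, and restate the precision as about 83 to 99% (Wilson); or
- keep the 10-point width, and replace 37 with 83 and 1,542 with about 3,458. The interval should then read about 88 to 98%, because a Wilson interval is not centred on 95%. Putting 73 and 3,042 instead would still miss the width under the planned method.

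Next to the existing shortfall statement, add the expected number of RIF-resistant cases as scenarios: about 10 to 13 (width about 29 to 33 points) at 20% culture positivity and 12% resistance in the capped group, taken as part of the 1,666; about 26 to 32 (about 17 to 20 points) if that whole group is culture-positive at 12% resistance; more if resistance among treatment failures is higher. State which assumptions each scenario uses.

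Use one label, primary or secondary, for both RIF sensitivity and RIF specificity in the synopsis, Table 1, section 10.1 and section 10.2. Either choice removes the contradiction; the choice is the sponsor's. Judge any shortfall for the later sub-study against the corrected number.

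Cost: protocol wording and a less favourable stated precision. No extra trial participants are needed, but a higher target would call for more banked specimens if the sub-study goes ahead.
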